1. INTRODUCTION

This SAP has been developed after review of the clinical study protocol (Final Version 2.0 dated 07 October 2020) and electronic case report form.

This SAP describes the planned analysis of the pharmacokinetic (PK), and safety and tolerability data from this study. A detailed description of the planned TFLs to be presented in the clinical study report (CSR) is provided in the accompanying TFL shells document.

In general, the analyses are based on information from the protocol, unless they have been modified by agreement with Loxo Oncology, Inc. A limited amount of information about this study (eg, objectives, study design) is given to help the reader's interpretation. This SAP must be finalized prior to the lock of the clinical database for this study. When the SAP and TFL shells are approved, they will serve as the template for this study's CSR.

This SAP supersedes any statistical considerations identified in the protocol; where considerations are substantially different, they will be so identified. If additional analyses are required to supplement the planned analyses described in this SAP, they may be performed and will be identified accordingly in the CSR. Any substantial deviations from this SAP will be agreed with Loxo Oncology, Inc. and identified in the CSR.

This SAP is written with consideration of the recommendations outlined in the International Conference on Harmonisation (ICH) E9 guideline *Statistical Principles for Clinical Trials* and ICH E3 guideline *Structure and Content of Clinical Study Reports*.^{1,2}

The document history is presented in [Appendix 1](#).

2. STUDY OBJECTIVES

2.1. Primary Objective

The primary objective of the study is to evaluate the PK profile of LOXO-305 in subjects with impaired hepatic function compared to matched-control healthy subjects.

2.2. Secondary Objective

The secondary objective of the study is to evaluate safety and tolerability of LOXO-305 in subjects with impaired hepatic function and matched-control healthy subjects.

3. STUDY ENDPOINTS

3.1. Primary Endpoints

The following PK parameters will be calculated whenever possible, based on the plasma concentrations of LOXO-305:

- maximum observed plasma concentration (C_{max})

-
- time to maximum observed plasma concentration (t_{max})
 - area under the concentration-time curve (AUC) from hour 0 to the last measurable concentration (AUC_{0-t})
 - area under the concentration-time curve from hour 0 extrapolated to infinity (AUC_{0-inf})
 - percentage extrapolation for AUC_{0-inf} (% AUC_{extrap})
 - apparent terminal elimination rate constant (λ_z)
 - apparent plasma terminal elimination half-life ($t_{1/2}$)
 - apparent systemic clearance (CL/F)
 - apparent volume of distribution at the terminal phase (V_z/F)
 - mean residence time extrapolated to infinity (MRT_{inf}).

In addition, a single blood sample will be collected predose to determine the fraction unbound (f_u) of LOXO-305 in plasma and, whenever possible, the following PK parameters will be calculated for unbound LOXO-305 using f_u : unbound C_{max} ($C_{max,u}$), unbound AUC_{0-t} ($AUC_{0-t,u}$), unbound AUC_{0-inf} ($AUC_{0-inf,u}$), unbound CL/F (CL/F, u), and unbound V_z/F ($V_z/F,u$).

3.2. Secondary Endpoints

Safety and tolerability will be assessed by monitoring adverse events (AEs), performing physical examinations and clinical laboratory evaluations, measuring vital signs, and recording electrocardiogram (ECGs).

4. STUDY DESIGN

This study is an open-label, nonrandomized, multi-center, single-dose, parallel-group study to determine the PK, safety, and tolerability of LOXO-305 administered orally at a dose of 200 mg to fasted adult males and females with mild, moderate, or severe impaired hepatic function and healthy subjects with normal hepatic function. Hepatic function will be classified based on the Child-Pugh (CP) classification of hepatic impairment.

Subjects will be recruited in this study so that up to 24 subjects with hepatic impairment (up to 8 subjects with mild impairment, up to 8 subjects with moderate impairment, and up to 8 subjects with severe impairment, per CP classification – assessed at Screening and verified at Check-in [Day -1]) and 8 to 24 subjects with normal hepatic function are enrolled, with the goal of having at least 6 subjects from each hepatic impairment group per CP classification and at least 6 subjects with normal hepatic function complete the study. Hepatically impaired subjects will be assigned to groups according to CP scores at Check-in (Day -1) to ensure stability of hepatic impairment and subject safety, as determined by the Investigator [or designee]. Subjects will be enrolled within the following groups based on their CP score at

[figure not shown]
Screening and Check-in (Day -1) as judged by the Investigator (or designee), Covance Medical Monitor, and Sponsor:

- Group 1: Matched-control healthy subjects with normal hepatic function;
- Group 2: Subjects with mild hepatic impairment (CP Class A, score of 5 or 6); •
- Group 3: Subjects with moderate hepatic impairment (CP Class B, score of 7 to 9);
- Group 4: Subjects with severe hepatic impairment (CP Class C, score of 10 to 15).

A parallel-design strategy will be adopted for the hepatic impairment groups, with interim reviews of the safety data after the first 2 subjects from Group 2 (mild hepatic impairment subjects) and Group 3 (moderate hepatic impairment subjects) and matched-control healthy subjects are enrolled and have completed all study-related assessments including the followup phone call.

A schematic of the study design is presented in [Figure 1](#).

Figure 1: Study Design

ICF = Informed Consent Form; PK = pharmacokinetic.

Note: Single oral dose of LOXO-305 at 200 mg administered orally after at least an 8-hour fast

Each matched-control healthy subject (Group 1) will be demographically matched (1:1) by age (\pm 10 years), body mass index (BMI) (\pm 20%), and sex to the completed hepatic impairment subject(s). Should another hepatic impairment subject be identified with whom an already enrolled healthy subject is demographically matched, the healthy subject may also be matched with that impaired subject as long as the impaired subject is in a different hepatic impairment group. Each subject with normal hepatic function may be matched with up to 1 subject within each hepatic impairment group.

The start of the study is defined as the date the first subject who is enrolled in the study signs an Informed Consent Form (ICF). Note that enrolled subjects are defined as those subjects who are assigned a dose of study drug; this definition excludes screen failure subjects. Replacement subjects may be enrolled only if deemed necessary by the Sponsor.

To assess their eligibility to enter the study, potential subjects will be screened within 28 days (Days -29 to -2) and admitted to the Clinical Research Unit (CRU) on Day -1 (Check-in). Subjects who are determined to be screen failures are permitted to be re-screened if the

Investigator (or designee), with agreement from the Covance Medical Monitor and the Sponsor, feels that the subject may meet eligibility criteria upon re-screen. Re-screened subjects will be provided a new subject number.

Subjects will be confined at the CRU from the time of Check-in (Day -1) until End of Treatment (EOT) on Day 8 upon completion of all PK and safety assessments or Early Termination (ET) if the subject discontinues. A follow-up phone call will occur for all subjects who received a dose of study drug (including subjects who are terminated early) 7 days (\pm 2 days) after EOT or ET. The duration of participation is expected to be approximately 46 days (Screening through follow-up phone call).

On the morning of Day 1, after at least an 8-hour fast, a single oral dose of 200 mg LOXO-305 will be administered with 240 mL of water. No food will be allowed for up to 2 hours postdose. Glucose tablets may be administered as needed for treatment of hypoglycemia. PK samples will be obtained through 168 hours postdose.

In this study, physical examinations, 12-lead ECGs, vital sign measurements, How Do You Feel? inquiries, clinical chemistry panel, coagulation parameters, hematology panel, urinalysis, and recording of concomitant medications will be performed at specified times during the study.

AEs and serious AEs (SAEs) will be collected beginning at informed consent. AEs will be reported throughout the study (ie, from signing of the ICF until End of Study [EOS], or until ET if the subject discontinues from the study and does not complete a follow-up phone call), either as subject medical history (if the event is reported as beginning prior to signing of the ICF or if the event occurs prior to study drug administration on Day 1 and is assessed as not related to study procedures by the Investigator [or designee]) or as AEs (if the event occurs after signing of the ICF but prior to study drug administration on Day 1 and is assessed as related to study procedures by the Investigator [or designee], or if the event occurs after study drug administration on Day 1 through EOT or ET regardless of relationship to study drug). From EOT or ET through EOS, only AEs assessed as related to study drug by the Investigator (or designee) are to be reported. All SAEs that develop from the time of ICF signing until EOS (or ET, if the subject discontinues from the study and does not complete a follow-up phone call) are to be reported. Study completion is defined as the time of the last subject's follow-up.

5. SAMPLE SIZE JUSTIFICATION

A total of up to 24 subjects with hepatic impairment (up to 8 subjects from each hepatic impairment group, per CP classification) and approximately 8 to 24 matched-control healthy subjects with normal hepatic function will be enrolled in the study with the goal of having at least 6 subjects from each hepatic impairment group per CP classification and at least 6 subjects with normal hepatic function complete the study. Of these hepatic impairment subjects enrolled per CP category, enrollment will also aim to have at least 4 subjects meet severe hepatic impairment criteria per National Cancer Institute-Organ Dysfunction Working Group (NCI-ODWG) classification, at least 4 subjects meet moderate hepatic impairment criteria per NCI-ODWG classification, and at least 4 subjects meet mild hepatic impairment

criteria per NCI-ODWG classification. The sample size chosen for this study was based upon precedent set by other PK studies of similar nature and was not based on power calculations to detect statistically significant differences among groups. This number is considered a sufficient sample size to evaluate the PK of LOXO-305 under various degrees of hepatic function.

6. STUDY TREATMENT AND HEPATIC FUNCTION GROUPS

The planned treatment administered for all subjects will be 200 mg LOXO-305.

The hepatic function group names and ordering to be used in the TFLs are presented in [Table 1](#) and [Table 2](#).

Table 1: Presentation of Hepatic Function Groups in TFLs by CP classification (Safety and PK)

Hepatic Function Group	Child-Pugh Classification	Abbreviation	Order in TFLs
Normal Hepatic Function	NA*	Normal	1
Mild Hepatic Impairment	5 or 6 points (Class A)	Mild	2
Moderate Hepatic Impairment	7 to 9 points (Class B)	Moderate	3
Severe Hepatic Impairment	10 to 15 points (Class C)	Severe	4

*Only subjects with hepatic impairment will have CP scores calculated at screening and Day -1. Hepatically impaired subjects will be assigned to groups according to CP scores at Check in (Day -1)

All hepatic function groups described above are the planned groups. The TFLs will reflect the actual hepatic function groups dosed based upon their CP score unless otherwise stated.

Table 2: Presentation of Hepatic Function Groups in TFLs by NCI-ODWG classification (PK)

Hepatic Function Group	NCI-ODWG Classification	Abbreviation	Order in TFLs
Normal Hepatic Function	Total Bilirubin: \leq ULN AST: \leq ULN *	Normal	1
Mild Hepatic Impairment	Total Bilirubin: > ULN to 1.5 x ULN AST: >ULN	Mild	2
Moderate Hepatic Impairment	Total Bilirubin: >1.5 to 3 x ULN AST: Any	Moderate	3
Severe Hepatic Impairment	Total Bilirubin: > 3 – 10 x ULN AST: Any	Severe	4

Abbreviations: AST = aspartate aminotransferase; NCI-ODWG = National Cancer Institute-Organ Dysfunction Working Group; ULN = upper limit of normal.

*Only subjects with hepatic impairment will have NCI-ODWG scores calculated at screening and Day -1. Hepatically impaired subjects will be assigned to groups according to NCI-ODWG scores at Check in (Day -1)

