3. INVESTIGATIONAL PLAN

3.1. Overall Study Design and Plan

This study is an open-label, nonrandomized, multi-center, single-dose, parallel-group study to determine the PK, safety, and tolerability of LOXO-305 administered orally at a dose of 200 mg to fasted adult males and females with mild, moderate, or severe impaired hepatic function and healthy subjects with normal hepatic function. Hepatic function will be classified based on the CP classification of hepatic impairment (Table 3).^{9,10}

Subjects will be recruited in this study so that up to 24 subjects with hepatic impairment (up to 8 subjects with mild impairment, up to 8 subjects with moderate impairment, and up to 8 subjects with severe impairment, per CP classification – assessed at Screening and verified at Check-in [Day -1]) and 8 to 24 subjects with normal hepatic function are enrolled, with the goal of having at least 6 subjects from each hepatic impairment group per CP classification and at least 6 subjects with normal hepatic function complete the study. Hepatically impaired subjects will be assigned to groups according to CP scores at Check-in (Day -1) to ensure stability of hepatic impairment and subject safety, as determined by the Investigator [or designee]. Subjects will be enrolled within the following groups based on their CP score at Screening and Check-in (Day -1) as judged by the Investigator (or designee), Covance Medical Monitor, and Sponsor:

- Group 1: Matched-control healthy subjects with normal hepatic function;
- Group 2: Subjects with mild hepatic impairment (CP Class A, score of 5 or 6);
- Group 3: Subjects with moderate hepatic impairment (CP Class B, score of 7 to 9);
- Group 4: Subjects with severe hepatic impairment (CP Class C, score of 10 to 15).

A parallel-design strategy will be adopted for the hepatic impairment groups, with interim reviews (as detailed in Section 8.2) of the safety data after the first 2 subjects from Group 2 (mild hepatic impairment subjects) and Group 3 (moderate hepatic impairment subjects) and matched-control healthy subjects are enrolled and have completed all study-related assessments including the follow-up phone call.

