3.2. Child-Pugh Classification

Per FDA Guidance¹² hepatic impairment will be classified as mild, moderate, or severe using the CP System (Table 3),^{9,10} and the parameters to determine the CP class for each subject with hepatic impairment will be collected at Screening and Check-in (Day -1). Further data analysis will be performed using NCI-ODWG classification (see Section 8).

Table 3: Child-Pugh Assessment of Hepatic Function

	Points Scored for Observed Findings		
	1	2	3
Hepatic encephalopathy grade ^a	0	1 or 2°	3 or 4°
Ascites ^b	Absent	Slight	Moderate
Serum bilirubin, mg/dL (μmol/L)	< 2 (< 34)	2 to 3 (34 to 50)	> 3 (> 50)
Serum albumin, g/dL (g/L)	> 3.5 (> 35)	2.8 to 3.5 (28 to 35)	< 2.8 (< 28)
International normalized ratio	< 1.7	1.7 to 2.3	> 2.3

Chronic Hepatic Impairment is classified into Child-Pugh (CP) class A to C, employing the added score of the 5 parameters in the table above.

Mild Impairment (CP-A): 5 or 6 points; Moderate Impairment (CP-B): 7 to 9 points; Severe Impairment (CP-C): 10 to 15 points.

^a In this study, hepatic encephalopathy is graded according to the following criteria:

- Grade 0: normal consciousness, personality, neurological examination, or normal electroencephalogram;
- Grade 1: restless, sleep disturbed, irritable/agitated, tremor, impaired handwriting, or 5 cycles per second waves;
- Grade 2: lethargic, time-disoriented, inappropriate, asterixis, ataxia, or slow triphasic waves;
- Grade 3: somnolent, stuporous, place-disoriented, hyperactive reflexes, rigidity, or slower waves;
- Grade 4: unarousable coma, no personality/behavior, decerebrate, or slow 2 to 3 cycles per second delta activity.

- Absent: No ascites is detectable by manual examination or by ultrasound investigation, if ultrasound investigation is performed;
- Slight: Ascites palpitation doubtful, but ascites measurable by ultrasound investigation, if performed;
- Moderate: Ascites detectable by palpitation and by ultrasound investigation, if performed;
- Severe: Necessity of paracentesis; does not respond to medication treatment.

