3.3. NCI-ODWG Classification

Subjects will also be classified according to NCI-ODWG criteria (Table 4).¹¹ Of these hepatic impairment subjects enrolled per CP classification, enrollment will also aim to have at least 4 subjects meet severe hepatic impairment criteria per NCI-ODWG classification, at least 4 subjects meet moderate hepatic impairment criteria per NCI-ODWG classification, and at least 4 subjects meet mild hepatic impairment criteria per NCI-ODWG classification.

^b Ascites is graded according to the following criteria:

^c A subject with hepatic encephalopathy of Grade 2 or above would not be admitted into the study.

Table 4: National Cancer Institute-Organ Dysfunction Working Group for Hepatic Dysfunction Criteria

	NCI-ODWG (Criteria Cri
Hepatic Impairment	Total Bilirubin	AST
Normal	≤ULN	≤ULN
Mild	> ULN to 1.5 x ULN	>ULN
Moderate	>1.5 to 3 x ULN	Any
Severe	> 3 - 10 x ULN	Any

Abbreviations: AST = aspartate aminotransferase; NCI-ODWG = National Cancer Institute-Organ Dysfunction Working Group; ULN = upper limit of normal.

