- 9. Considered to have mild, moderate, or severe hepatic impairment (of any etiology) that has been clinically stable (no acute episodes of illness due to deterioration in hepatic function) for at least 1 month prior to Screening per the Investigator (or designee), Sponsor, and Covance Medical Monitor and are likely to remain stable throughout EOS. To be classified as having hepatic impairment, subjects must have a CP score of 5 to 6 (mild), 7 to 9 (moderate), or 10 to 15 (severe), with known medical history of liver disease (with or without a known history of alcohol abuse).
- 10. Currently on a stable medication regimen, defined as not starting new drug(s) or significantly changing drug dosage(s) within 14 days prior to Day 1. Concomitant medications administered within 30 days prior to Day 1 must be approved by the Investigator (or designee), Covance Medical Monitor, and Sponsor. Subjects must be able to withhold the use of these medications for 2 hours predose and 4 hours postdose on Day 1, unless approved by the Covance Medical Monitor, Investigator (or designee) and Sponsor.
- 11. Non-hepatic abnormal laboratory values must be not clinically significant, as judged by the Investigator (or designee), Covance Medical Monitor, and Sponsor.
- 12. Anemia secondary to hepatic disease will be acceptable if hemoglobin is ≥ 8 g/dL and anemia symptoms are not clinically significant. Must have $\geq 35,000$ platelets.

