- 36. eGFR of < 90 mL/minute/1.73m² calculated using the CKD-EPI equation at Screening or Check-in (Day -1) for subjects with mild or moderate hepatic impairment or eGFR of < 60 mL/minute/1.73m² calculated using the CKD-EPI equation at Screening or Check-in (Day -1) for subjects with severe hepatic impairment. Rechecks of out-of-range eGFR values that are not clinically significant (as determined by the Investigator [or designee]) will be permitted up to 2 times during Screening and Check-in (Day -1) to confirm eligibility for study participation if the values fall within the range stated above.
- 37. Values outside the normal ranges for creatine kinase, LFTs, amylase, and lipase may be acceptable as consistent with the subject's hepatic condition (if stable for 1 month prior to Screening), and if the Investigator (or designee) and Sponsor feel that the results are not clinically significant (based on age and hepatic impairment status).
- 38. Known ongoing alcohol and/or drug abuse within 1 month prior to Screening, or evidence of such abuse as indicated by the laboratory assays for drugs of abuse (including alcohol) conducted during Screening and/or at Check-in (Day -1). Tests for drugs of abuse (aside from cotinine) must be negative at both Screening and Check-in (Day -1) unless the positive drug screen is considered to be due to the use of a prescription drug which is approved by the Covance Medical Monitor, Investigator (or designee), and Sponsor.
- 39. Smoking more than 10 cigarettes per day or equivalent (eg, e-vapor cigarette, pipe, cigar, chewing tobacco, nicotine patch, nicotine gum) throughout the confinement period of the study (EOT or ET); unable or being unwilling to refrain from the use of tobacco- or nicotine-containing products for 2 hours prior to dosing and 4 hours after dose administration on Day 1.
- 40. History of unstable diabetes mellitus (as evidenced by HbA1c \geq 10.0% at Screening). Medications for the treatment of diabetes mellitus must be reviewed and approved by the Investigator (or designee), Covance Medical Monitor, and Sponsor.
- 41. History of cancer within the past 5 years (except localized basal cell, squamous, or in situ cancer of the skin).
- 42. Has a portal systemic shunt.

Protocol

- 43. Has required new medication for hepatic encephalopathy within the 6 months prior to Check-in (Day -1).
- 44. Recent history of paracentesis (within 30 days prior to Screening).

4.5. **Subject Number and Identification**

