Appendix 4: Schedule of Assessments

Covance Study: 8419691

Study Procedures ^a	Screening (Days -29 to -2)	Check-in (Day -1)	Study Conduct		CRU Discharge/ EOT or ET ^u	Follow-up Phone Call (EOS)
			Day 1	Days 2 to 7	Day 8	7 (± 2) days post EOT or ET ^w
Confined to the CRU		X	X	X	X	
Inclusion/Exclusion Criteria	X	X				
Informed Consent	X					
Demographics	X					
CP Class Scoreb	X	X				
NCI-ODWG Class Scoreb	X	X				
Medical History	X	Xc				
Height/Weight/BMI	X ^d	X ^d				
Physical Examination ^e	X	X			X	
12-Lead ECG ^f	X	X	X		X	
Vital Signs ^g	$X^{h,i}$	$X^{h,i}$	Xi	X	$X^{h,i}$	
HDYF? Inquiry ^j	X	X	X	X	X	X
AEs/SAEs ^k	X	X	X	X	X	X
LOXO-305 Dose ¹			X			
CCI						
Clinical Laboratory Evaluations ^o	X	X		Xv	Xv	
COVID-19 Test ^p	X	X				
eGFR	X	X				
Hepatitis and HIV Screen	X					
HbA1c Test	X					
Drug Screen ^q	X	X				
Prior and Concomitant Medications ^r	X	X	X	X	X	X
Serum Pregnancy Tests	X	X		Xv	X ^v	
FSH Test ^t	X					
TSH Test	X					

Abbreviations: AE = adverse event; BMI = body mass index; BP = blood pressure; COVID-19 = SARS-CoV-2; CP=Child-Pugh; CRF = Case Report Form; CRU = Clinical Research Unit; ECG = electrocardiogram; eGFR = estimated glomerular filtration rate EOS = End of Study; EOT = End of Treatment; ET = Early Termination; FSH = Follicle Stimulating Hormone; HbA1c = hemoglobin A1c; HDYF? = How Do You Feel?; HIV = human immunodeficiency virus; ICF = Informed Consent Form; NCI-ODWG = National Cancer Institute – Organ Dysfunction Working Group; PK = pharmacokinetic; SAE = serious adverse event; TSH = Thyroid Stimulating Hormone; UA = urinalysis.

a. For details on study procedures, see Section 7.

b. Subjects with hepatic impairment only. Child-Pugh and NCI-ODWG scores will be calculated at Screening and Check-in (Day -1); hepatically impaired subjects will be assigned to groups according to CP scores at Check-in (Day -1) to ensure stability of hepatic impairment and subject safety, as determined by the Investigator (or designee).

c. Interim medical history only.

Covance Study: 8419691 Protocol Reference: LOXO-BTK-20012

- d. Height collected at Screening only, body mass index based on Screening height.
- e. A complete physical examination will be performed at Screening and EOT (Day 8, 168 hours postdose) or ET. An abbreviated physical examination will be performed at Check-in (Day -1).

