Appendix 5: Protocol Amendment Summary of Changes

Protocol Version 2.0 (dated 7th October 2020) incorporated the following changes in Protocol Version 1.0 (dated 7th August 2020):

- Additional data from non-clinical studies with LOXO-305 has been added to Section 1.2, *Nonclinical Pharmacokinetics and Toxicology*.
- Additional data from clinical studies with LOXO-305 has been added to Section 1.4, *Summary of Clinical Experience*, Section 1.4.1, *Safety*, and Section 1.6, *Risk Assessment*.
- The Protocol has been updated to allow glucose tablets to be administered as needed for treatment of hypoglycaemia during the study as a safety precaution.
- The number of subjects aimed to be enrolled into each National Cancer Institute's Organ Dysfunction Working Group (NCI-ODWG) classification for hepatic impairment has been clarified throughout the Protocol from a minimum of 4 subjects with mild and moderate hepatic impairment by NCI-ODWG classification, to at least 4 subjects meeting moderate hepatic impairment criteria per NCI-ODWG classification, and at least 4 subjects meeting mild hepatic impairment criteria per NCI-ODWG classification.
- Table 4, National Cancer Institute-Organ Dysfunction Working Group for Hepatic Dysfunction Criteria has been corrected such that the criteria for mild hepatic impairment and severe hepatic impairment are consistent with the criteria used in the publication cited in the Protocol.
- The requirements for hepatitis C virus antibody testing have been clarified throughout the Protocol to state that this will be conducted in healthy matched-control subjects only to be consistent with Section 4.1, *Screening Procedures*, #13.
- The requirements for hepatitis B virus testing have been clarified throughout the Protocol to state that it will be performed using an immunoglobulin M (IgM) core antibody test.
- The requirements for oral temperature measurements to be taken have been revised throughout the Protocol, to allow any type of temperature measurements to be taken to provide flexibility to study sites.
- The duration of contraceptive requirements for male subjects without documentation of sterilization has been clarified to state that male subjects must follow 1 of the contraception methods listed under inclusion criterion #5b from Day 1 through 6 months after Day 1.

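### The NCI-ODWG Mild row has no 'and' or 'or': read as 'and', two bilirubin/AST combinations open to eligible impaired subjects have no class (minor; supplementary outputs only)

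*SAP*

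**What the plan says.** Protocol section 3.3 states: "Subjects will also be classified according to NCI-ODWG criteria (Table 4"). SAP section 6, Table 2, carries the same four rows:

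- Normal: bilirubin at or below ULN; AST at or below ULN.
- Mild: "Total Bilirubin: > ULN to 1.5 x ULN AST: >ULN".
- Moderate: bilirubin above 1.5 to 3 times ULN; any AST.
- Severe: bilirubin above 3 to 10 times ULN; any AST.

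Neither table joins the two Mild conditions with a word, and no footnote or other section does so. Protocol Appendix 4, footnote b, fixes the timing: "Child-Pugh and NCI-ODWG scores will be calculated at Screening and Check-in (Day -1"). The footnote to SAP Table 2 then takes the class from the Check-in values.

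The class is used in several places in the SAP: the disposition summary (8.2), the baseline summary (8.3), the PK concentration, PK parameter and protein-binding summaries (8.5.3) and an ANCOVA (8.5.3.1). SAP section 5 also sets an enrolment aim of at least 4 subjects in each of the three impaired NCI-ODWG classes. Protocol section 3.2 presents all this as supplementary to Child-Pugh: "Further data analysis will be performed using NCI-ODWG classification (see Section 8").

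**The concern.** A classification table used for analysis should give each subject one class. This one does not, whichever plain reading of the Mild row is taken.

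'And' is the more literal reading. The Normal row has the same layout and must require both conditions, or a subject with very high bilirubin and normal AST would count as Normal. Moderate and Severe mark AST as irrelevant by printing 'Any'; Mild does not. But 'and' leaves holes on either side of the Mild row. 'Or' fills them and creates overlaps with the two higher classes.

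Under 'and', an impaired subject who falls in a hole has no column in the NCI-ODWG PK and protein-binding summaries and no factor level in the NCI-ODWG ANCOVA, and cannot count toward the aim of 4 Mild subjects. Neither document says what to do with such a subject. More than one site applies the table (protocol 3.1: "This study is an open-label, nonrandomized, multi-center, single-dose, parallel-group study"), so the same laboratory values could also be scored in different ways.

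**Working it through.** The documents contain no figure to reproduce here; the check is of the table's logic.

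**Step 1. Enumerate the cells.** Four bilirubin bands up to 10 times ULN by two AST states give 4 x 2 = 8 cells. These are cells, not subjects.

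| Bilirubin (x ULN) | AST | Mild as 'and' | Mild as 'or' | 'Or', highest class met |
|---|---|---|---|---|
| ≤1 | ≤ULN | Normal | Normal | Normal |
| ≤1 | >ULN | **none** | Mild | Mild |
| >1 to 1.5 | ≤ULN | **none** | Mild | Mild |
| >1 to 1.5 | >ULN | Mild | Mild | Mild |
| >1.5 to 3 | ≤ULN | Moderate | Moderate | Moderate |
| >1.5 to 3 | >ULN | Moderate | **Mild and Moderate** | Moderate |
| >3 to 10 | ≤ULN | Severe | Severe | Severe |
| >3 to 10 | >ULN | Severe | **Mild and Severe** | Severe |

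- 'And': 6 cells with one class, 2 with none, 0 with two.
- 'Or': 6 cells with one class, 0 with none, 2 with two.
- 'Or, highest class met': all 8 cells with one class. Neither document prints this rule.

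The first and third readings differ only in the two unclassified cells. Moderate and Severe membership up to 10 times ULN is the same under both.

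**Step 2. Above 10 times ULN.** No row covers this. 'And' gives no class for either AST state. 'Or' gives none when AST is not raised and, oddly, Mild when it is. No bilirubin ceiling applies to impaired subjects, so the case is possible, though remote.

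**Step 3. Can eligible subjects reach the two holes?**

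- Impaired subjects enter on Child-Pugh score (inclusion criterion 9): "subjects must have a CP score of 5 to 6 (mild), 7 to 9 (moderate), or 10 to 15 (severe"). The five items in protocol Table 3 do not include AST.
- Exclusion criterion 37 permits abnormal liver tests but does not require them: "Values outside the normal ranges for creatine kinase, LFTs, amylase, and lipase may be acceptable". AST may therefore be raised or not.
- Bilirubin below 2 mg/dL scores 1 point. The documents give no ULN. Assuming 1.0 to 1.3 mg/dL, 1.5 x 1.0 = 1.5 and 1.5 x 1.3 = 1.95 mg/dL, so both holes lie inside the 1-point band. At an assumed ULN of 1.5 mg/dL, 1.5 x 1.5 = 2.25 mg/dL, and the top of the second hole scores 2 points; such a subject is still eligible.
- With 1 point for bilirubin, the lowest total is 1+1+1+1+1 = 5. The highest is 1+2+3+3+3 = 12, with encephalopathy capped at 2 points because Grade 2 or above is not admitted. Totals of 5 to 12 touch all three Child-Pugh classes.

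Both holes are open to eligible impaired subjects. Healthy controls are not affected: exclusion criterion 23 bars AST or bilirubin above ULN, so they all fit the Normal row.

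**Step 4. Slack against the class aims.** The three aims total 4+4+4 = 12. Targeted impaired completers number 3 x 6 = 18 and maximum impaired enrolment is 24, leaving 18-12 = 6 to 24-12 = 12 spare. An unclassified subject need not make the Mild aim fail.

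**The case against.** The best defence is that this is an ordered severity scale on which bilirubin alone sets the two upper classes, so assigning the highest class met is a natural reading, and it leaves no hole or overlap up to 10 times ULN. The protocol also adopts a published classification, and Appendix 5 names that source as the standard for Table 4 ("consistent with the criteria used in the publication cited in the Protocol"). Under protocol section 4.2 the medical monitor reviews screening evaluations, and the medical monitor and sponsor approve each subject before dosing, so sites do not act without oversight. Much of this stands, and it keeps the point minor. It does not supply the rule: the tie-break is unprinted, central review has no stated criterion to apply, and the printed table is what a programmer will code.

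Four stronger readings are tempting, and the documents do not support them.

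- A reader might infer a definite loss of precision for Mild versus Normal. That would need subjects counted as Mild under 'or' and then analysed under 'and'. The SAP takes the Check-in class, the two tables have the same rows, and no section describes a second derivation.
- A reader might infer that unclassified subjects vanish from every NCI-ODWG output. SAP 8.1.1 adds a 'missing' category to categorical summaries, which may hold them there, for example in the baseline tabulation. It does not give them a place in the by-class PK tables or the ANCOVA.
- A reader might infer room to choose a class after seeing exposure. The class is scored at Screening and Check-in, before dosing.
- A reader might infer that the NCI-ODWG ANCOVA lacks a reference group. SAP 8.5.3.1 names the normal group as reference in the Child-Pugh model that this analysis is to resemble.

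**Conclusion.** Wrong as written, but minor. Followed literally, the Mild row leaves 2 of 8 bilirubin-by-AST cells up to 10 times ULN without a class; read as plain 'or', it puts 2 others in two classes. That conclusion rests on the printed tables alone. The claim that eligible subjects can reach the holes rests on the eligibility criteria, with an assumed ULN used only to locate the Child-Pugh bilirubin points.

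How many subjects are affected cannot be worked out from the documents and may be 0. The reach is the supplementary NCI-ODWG outputs and the aim for the Mild class. The Child-Pugh paired analysis, the Child-Pugh ANCOVA and the safety outputs do not depend on this table.

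**What to change.** Before database lock:

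1. Check protocol Table 4 and SAP Table 2 against the publication the protocol cites.
2. Restate the Mild row in both so that each bilirubin/AST combination up to 10 times ULN falls in exactly one class. If the source agrees, one wording is: bilirubin at or below ULN with AST above ULN, or bilirubin above ULN to 1.5 times ULN with any AST. A bare 'or' is not enough, because it leaves the overlaps with Moderate and Severe.
3. Add a sentence saying where bilirubin above 10 times ULN is placed.
4. Apply that single rule to the Check-in values for every impaired subject.

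The cost is one row of wording in two tables and one sentence. No new data are needed, since bilirubin and AST are already part of the Check-in chemistry panel.
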